## 7.2 SUBJECT ACCOUNTABILITY

The number of subjects screened and the number (percentage) of subjects who failed screening (i.e., subjects who consented to participate in the clinical study but were not subsequently randomized) and the reasons for screen failure will be summarized.

In addition, the number of subjects who withdrew from the study and discontinued the investigational product will be summarized by discontinuation reason (including discontinuation due to COVID-19 pandemic).

The information including demography and screen failure details will be listed. Subjects with dose interruptions affected by the COVID-19 pandemic will also be noted in the listing.

## 7.3 PROTOCOL DEVIATIONS

A full list of protocol violations and deviations will be compiled and reviewed by the clinical team to identify important violations/deviations before final database lock. For violations at study entry, subjects will be assessed against the inclusion and exclusion criteria of the protocol. For on-study deviations, compliance with the protocol will be examined using blinded review of the database with regard to prohibited therapies, and timing and availability of planned assessments.

## 7.4 INVESTIGATIONAL PRODUCT ADMINISTRATION

### 7.4.1 Extent of Exposure and Treatment Compliance

The length of exposure to investigational product (as BIO89-100 or placebo) will be calculated as the number of days from the first dose to the last dose of double-blind investigational product administration +7, regardless of if the subject missed one or more doses of investigational product.

Total dose administered (mg) is calculated as number of injections received x dose (mg) of the investigational product contained in the injection.

Overall study treatment compliance will be calculated at the end of treatment as (total injections administered /total injections expected x 100%. Total injections expected is defined as the total number of injections protocol defined until the end of treatment.

The length of exposure, number of actual drug injections and number of missed injections, total dose administered, and overall study treatment compliance will be summarized by treatment group using descriptive statistics for the safety population. The investigational product administration and compliance data, including reasons for poor compliance, will be listed for each subject.

### 7.4.2 Medical History

General medical history and background therapy will be summarized by treatment group, as well as overall, for FAS population and presented in a by-subject listing. Where appropriate, terms will be coded using the Medical Dictionary for Regulatory Activities (MedDRA) Version 23.0 or higher.

### 7.4.3 Demographics and Baseline Characteristics

The following demographic and baseline characteristics will be summarized by treatment group, as well as overall, for Safety Analysis Set and for Full Analysis Set:

- Age in years and by age group (21-<65, >=65-<75 and >=75)
- Gender
- Race
- Ethnicity
- Height (cm), weight (kg), weight group, body mass index (kg/m^2), BMI group (< 25, 25 -< 30,  $\geq$  30 kg/m^2), [REDACTED]  
[REDACTED]
- systolic and diastolic blood pressure (mmHg),

- Serum lipids, lipoproteins and apolipoproteins (TG [mg/dL], [redacted] [mg/dL], VLDLC [mg/dL], VLDL-TG [mg/dL], LDL-C [mg/dL], HDL-C [mg/dL], non-HDL-C [mg/dL], [redacted] [mg/dL], ApoB [mg/dL], [redacted] [mg/dL], [redacted] [mg/dL], [redacted])
- hsCRP [g/dL]), Adiponectin, fasting plasma glucose, [redacted]  
[redacted]
- ALT (U/L), AST (U/L)
- TG <750 mg/dL or  $\geq$ 750 mg/dL (8.47 mmol/L)
- Whether or not the subject is receiving background therapy (e.g., prescription fish oil and/or statins)
- History of Type 2 Diabetes
- History of hypertension
- History of Non-alcoholic fatty liver disease (NAFLD)
- History of Nonalcoholic steatohepatitis (NASH)
- Estimated Glomerular Filtration Rate (eGFR) category (normal:  $\geq$ 90 mL/min/1.73m^2; mild Renal Impairment: 60-89 mL/min/1.73m^2; moderate Renal Impairment: 30-59 mL/min/1.73m^2, and severe Renal Impairment: 15-29 mL/min/1.73m^2)
- MRI-PDFF [redacted]

Data will be summarized using descriptive statistics for continuous variables and using counts and percentages for categorical variables by treatment group and overall.

Hepatitis B surface antigen (HBsAg), hepatitis C virus (HCV), and serum pregnancy test (only for females of childbearing potential), follicle stimulating hormone (FSH) urine pregnancy test on Day 1 and thyroid-stimulating hormone (TSH) will be presented [redacted]  
[redacted]

#### 7.4.4 Prior, Baseline and Concomitant Medication/Procedure

Medications will be coded using WHO Drug (March, 2020 or later). The frequency of use of prior medications and use of concomitant medications will be summarized by treatment group, as well as overall, for the safety population according to Anatomical Therapeutic Chemical (ATC) class and preferred term. Prior and concomitant medications will be listed for each subject.

Prior and concomitant procedures will be listed.

## 7.5 EFFICACY ANALYSIS

The objective for the primary efficacy analyses is to evaluate the effect of BIO89-100 on TG reduction after the 8-week treatment period. The analyses consist of comparisons between the BIO89-100 groups and placebo as below:

1. A pooled BIO89-100 group combining all dose groups will be compared with the placebo to evaluate the overall effectiveness of BIO89-100
2. Individual BIO89-100 dose groups will be compared with the placebo group separately to evaluate the effectiveness of BIO89-100 at a specific dose

The study is considered positive and meeting the primary objective if any of the comparisons above is statistically significant.

All efficacy analysis will be performed using the FAS unless otherwise specified. Analyses comparing the placebo group and the pooled BIO89-100 group will be stratified if the sample size permits. The analyses comparing the placebo and individual dose group will not be stratified due to anticipated small size.

### 7.5.1 Analysis of Primary Efficacy endpoints

The primary endpoint is the percent change in TG at Week 8 from baseline. The TG value at week 8 is defined as the average of TG values at [REDACTED]

[REDACTED] In case of missing TG value at [REDACTED] the non-missing result will be used as the week 8 TG. The primary efficacy analysis will be performed using a mixed model with repeated measure (MMRM). The model includes the treatment group, baseline TG values, background therapy use, visit, visit and treatment interaction. The model will be fitted using all planned visits up to Week 8.

If the mixed model assumption of the MMRM method is severely violated, the non-parametric van Elteren test stratified by baseline TG level and background lipid therapy will be used to test the treatment difference using the pooled data. The location shift estimate, and Hodges-Lehmann 2-tailed 95% confidence interval will be presented. For the comparison between the individual dose group and the placebo, the unstratified Wilcoxon rank-sum test will be used instead due to the low sample size.

The primary efficacy analysis will be repeated in the subgroups (as noted in [Section 4.7](#)).

[REDACTED]  
[REDACTED]  
[REDACTED]  
[REDACTED]

[REDACTED]  
[REDACTED]  
[REDACTED]

[REDACTED]

[REDACTED]

[REDACTED]

[REDACTED]

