## 9.2. Sample Size Determination

The effect of BIO89-100 on the percentage change from baseline in TG is estimated based on prior clinical studies evaluating BIO89-100 and other TG lowering agents:

Based on these results, it is estimated that the SD of the percent change in TG at Week 8 is  $\sim$ 40%. With 18 subjects in the placebo group and each BIO89-100 dose group, there would be at least 86% power to detect a 45% difference in TG between each BIO89-100 dose group and placebo at the 2-sided alpha level of 0.05, assuming 50% reduction in BIO89-100 dose group and 5% in the placebo group.

Fatty liver has been shown to be significantly associated with moderately severe or severe acute pancreatitis (Yoon, et al. 2017). Hence, another focus of this study is to assess the BIO89-100 effect on reducing liver fat as assessed by MRI-PDFF in the SHTG population, with or without concurrent stable fibrate therapy. In Study BIO89-100-002 (Part 1), BIO89-100 (27 mg QW) reduced liver fat as assessed by MRI-PDFF up to 60%. In the main cohort not on concomitant fibrate therapy, a sample size of ~30 subjects (e.g., ~33% of the main cohort total sample size, ~6 placebo vs ~24 pooled BIO89-100) is estimated to provide ~89% power to detect a difference of at least 50% mean percentage reduction in MRI-PDFF at Week 8 compared to placebo, using a significance level of 0.05 (2-sided). These calculations are based on an assumption that the percentage change from baseline in MRI-PDFF is normally distributed with a standard deviation of no greater than 30%, as estimated from data in Study BIO89-100-002. In the fibrate expansion cohort, assuming a difference of 50% mean percentage reduction in MRI-PDFF at Week 8

compared to placebo, a standard deviation of no greater than 30% under normal assumption, and a significance level of 0.05 (2-sided), the planned sample size of 18 subjects per group will have >99% power to detect such a mean difference.

This sample size assessment incorporates approximately 10% of subjects lost to follow-up.

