## 4 STUDY ENDPOINTS AND COVARIATES

## 4.1 PRIMARY EFFICACY ENDPOINT

- Percentage change in serum TG from baseline to Week 8

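### The primary analysis can move from the MMRM to a rank test on an undefined trigger, and the readable SAP does not say whether residual variance may differ by treatment group

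*SAP*

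**What the plan says.** SAP section 7.5.1 defines the outcome on the raw scale: "The primary endpoint is the percent change in TG at Week 8 from baseline". The analysis is an MMRM, and its terms are listed: "The model includes the treatment group, baseline TG values, background therapy use, visit, visit and treatment interaction". The readable text names no covariance structure and does not say whether variance may differ by group. It also does not say whether each dose is fitted with placebo alone or all arms share one model.

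The same section makes the method conditional: "If the mixed model assumption of the MMRM method is severely violated", the pooled comparison moves to a stratified van Elteren test. For single doses, "the unstratified Wilcoxon rank-sum test will be used instead due to the low sample size". The estimate changes too: "The location shift estimate, and Hodges-Lehmann 2-tailed 95% confidence interval will be presented".

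The planning values are in Protocol section 9.2 and SAP section 3.5: an SD of about 40% and 18 subjects per group, "assuming 50% reduction in BIO89-100 dose group and 5% in the placebo group". The protocol (section 9.4.2) had ANCOVA as primary and an MMRM with unstructured covariance as sensitivity. SAP section 1 says that the SAP prevails where the two differ.

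**The concern.** A primary method that depends on an undefined judgement is not fully prespecified. If the judgement is made with treatment codes or results in view, the analyst can in effect choose between two tests. The SAP sets numeric triggers for lesser choices: more than 10% missing data (6.1.2), strata under 5 subjects (7.5.2), subgroups under 33% (4.7). It asks for blinded review of on-study protocol deviations (7.3). It states neither for this choice.

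The switch also changes the quantity estimated. For a single dose, a mean difference adjusted for baseline TG and background therapy becomes an unadjusted location shift.

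There is a separate question about variance. Percent change cannot go below -100%, so arms with large reductions may have less spread than placebo. A model with one variance for all groups would then understate the uncertainty in the placebo mean. What is at stake is the interval for the pooled comparison and the per-dose tests meant to inform Phase 3 dose selection (Protocol 4.2).

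**Working it through.** **1. The plan's own power figure.** Inputs: difference 45, common SD 40, two-sided alpha 0.05, and 18 per group less about 10%, so 16. SE = 40 × √(2/16) = 14.14; 45/14.14 = 3.18. The noncentral t with 30 df gives 86.8%, which reproduces the stated figure of at least 86%. Without losses (18 per group) it is 90.6%.

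**2. The floor.** Active: (-100 + 50)/40 = -1.25, so a normal model puts 10.6% below -100%, or 0.106 × 18 ≈ 1.9 subjects per arm. Placebo: (-100 + 5)/40 = -2.375, or 0.9%. The active-arm planning values cannot describe a normal distribution.

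**3. Does that alone damage the model?** Simulation: lognormal Week 8/baseline ratio, five arms of 18, one pooled Week 8 variance, no covariates, complete data. With mean ratios 0.95 and 0.50 and SD 0.40 in every arm, 95% coverage is 94.5% to 95.1%, error for an inactive dose is 5.7%, and power is about 90%. Little harm.

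**4. The switch.** Error for an inactive dose (6,000 runs, Monte Carlo SE about 0.3 points; all-arm model):

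| Scenario | Model | Wilcoxon | Smaller p | Shapiro rule, p<0.05 | Shapiro rule, p<0.001 |
|---|---|---|---|---|---|
| All arms alike | 4.6% | 4.6% | 6.4% | 4.7% | 4.9% |
| SD 40 in every arm, three other doses active | 5.8% | 4.7% | 7.4% | 4.8% | 5.2% |
| Active SD 21, three other doses active | 13.9% | 5.0% | 14.2% | 6.2% | 8.9% |

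Repeat runs of the smaller-p strategy without unequal variance gave 6.2% to 7.3%. The Shapiro rule fires in 94%, 99% and 91% of trials at p<0.05, and in 66%, 91% and 64% at p<0.001. With skewed data of this kind, a conventional check would call for the switch in most trials.

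**5. Change of estimate.** With SD 40 in every arm, the Hodges-Lehmann target is -45.4, against a mean difference of -45. With active SD 21 it is about -40, and its interval covers the mean difference 91.9% of the time.

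**6. Common variance, pooled comparison.** Assumptions: all doses at -50%, placebo SD 40, main-cohort sizes 72 versus 18. An SD proportional to the mean gives an active SD of 40 × 0.50/0.95 = 21.
- True variance of the difference: 1600/18 + 441/72 = 95.0.
- Common-variance version: (17 × 1600 + 71 × 441)/88 = 664.9; × (1/18 + 1/72) = 46.2.
- SE ratio: √(46.2/95.0) = 0.697. Effective multiplier: 1.987 × 0.697 = 1.385, so coverage is about 83%.
- At SD 30: √(71.9/101.4) = 0.842; 1.987 × 0.842 = 1.673, so about 91%.

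Lognormal simulation (40,000 runs) gives 82.6%, 86.5%, 90.4%, 92.7% and 94.4% at active SD 21, 25, 30, 35 and 40. Group-specific variance gives 93.7% to 94.5%. With a fully enrolled fibrate cohort (90 versus 36), coverage at SD 21 is 87.1%.

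**7. Common variance, single inactive dose beside three active ones (SD 21).** In one five-arm model the pooled variance is (2 × 1600 + 3 × 441)/5 = 904.6. SE ratio: √(904.6/1600) = 0.752; 1.988 × 0.752 = 1.495, so error is about 13.5%. Simulation gives 13.8% to 14.3%. Fitting placebo with that dose alone gives 4.8% to 4.9%.

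**8. Log scale.** If log-scale SD is equal across arms (0.404), error for an inactive dose is 4.8%. If raw SD is 40 in every arm, log SDs are 0.40 and 0.70, error falls to 0.4%, and power for a -30% dose drops from 49% to 40%.

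**The case against.** The strongest reply has four parts.

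- A reader might infer that the plan's own figures already breach the model's assumptions, so that its intervals and error rates are wrong. The documents do not support that. The figures show non-normality only, and with their single SD of 40 the error and coverage stay near nominal (step 3). Nothing shows the breach to be severe, since the term is undefined.
- The error of about 14% needs an active SD of 21, which the plan does not state, and one model for all arms, which the readable text does not specify. SAP section 7.5 says that the doses are compared with placebo separately, so fits of placebo plus one dose are a fair reading. This stands. It does not remove the exposure of the pooled comparison, where unequal group sizes are part of the design.
- The figure of 6% to 7% assumes that the smaller p-value is taken. The SAP describes a switch based on assumptions, and a fixed diagnostic rule keeps error at 4.7% to 5.2% when spreads are equal. This is right, and it is the reason to fix the rule or remove it.
- Lines after the switch text and the whole SAS appendix are redacted. A trigger, a covariance structure or group-specific variance may be there, so the criticism is limited to the readable text.

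The simulated arms of 18 also differ from the SAP's, which add fibrate-cohort subjects to placebo and 27 mg. The direction of the result is unchanged.

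**Conclusion.** The point holds as a cheap improvement to the plan. In the readable text, the primary test and its estimate hang on an undefined condition that realistic TG data would often meet. If the choice is free, per-dose error is about 6% to 7% instead of 5%.

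The variance part is conditional. If active and placebo SDs are both 40, a common variance does no material harm (94% coverage). If spread shrinks in effective arms, pooled-comparison coverage falls to about 90% at SD 30 and 83% at SD 21. Per-dose error of about 14% arises only at SD 21 with all arms in one model. These results rest on lognormal data, no covariates and complete follow-up.

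A reader might also conclude that the analysis must move to the log scale. That does not follow: it changes the declared arithmetic endpoint and is badly conservative if raw SDs are equal. The rule that any one of five unadjusted comparisons makes the study positive is a separate matter and adds no weight here.

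**What to change.** In SAP section 7.5.1:

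1. Delete the conditional switch and fix one primary method before unblinding.
2. Always report van Elteren (pooled) and Wilcoxon (per dose) with the Hodges-Lehmann interval, labelled as sensitivity analyses.
3. State the covariance structure and whether each comparison is a separate fit. Let residual variance differ by treatment group, at least active versus placebo. An unstructured covariance alone lets variance differ by visit, not by group.
4. Keep percent change as the endpoint. An MMRM on the log ratio may be added as a sensitivity analysis.

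If the redacted text already covers item 3, only items 1 and 2 are needed. The cost is SAP wording, a little more programming, slightly wider intervals, and more variance parameters to estimate in small arms.

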### 3.5 SAMPLE SIZE CONSIDERATIONS

The effect of BIO89-100 on the percentage change from baseline in TG is estimated based on prior clinical studies evaluating BIO89-100 and other triglyceride lowering agents. [REDACTED]

[REDACTED]

[REDACTED]

[REDACTED]

[REDACTED]

[REDACTED]

[REDACTED]

[REDACTED]

[REDACTED]

Based on these results, it is estimated that the SD of the percent change in TG at Week 8 is approximately 40%. With 18 subjects in the placebo group and each BIO89-100 active treatment group, there would be at least 86% power to detect a 45% difference in TG between each BIO89-100 active treatment group and placebo at the 2-sided alpha level of 0.05, assuming 50% reduction in BIO89-100 dose group and 5% in the placebo group. This sample size assessment incorporates approximately 10% of subjects will be lost to follow-up.

Approximately 90 subjects are planned to be enrolled in the main cohort, with 18 subjects in each of the BIO89-100 active treatment groups (9 mg QW, 18 mg QW, 27 mg QW, or 36 mg Q2W) and in the placebo group. The study aims to enroll ~33% of subjects (~30 subjects total) in the main cohort with a baseline MRI-PDFF  $\geq$  6%. Approximately 36 subjects are planned to be enrolled in the fibrate expansion cohort (18 in each treatment group) with all subjects having baseline MRI-PDF  $\geq$  6%. Subjects who terminate early in either cohort may be replaced at Sponsor's discretion.

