#### 4.7 COVARIATES AND SUBGROUPS

- TG  $<750$  mg/dL or  $\geq 750$  mg/dL
- Background lipid medication (Yes, No)
- Type of background lipid medication (use of statin (including combo therapy), use of fibrate therapy, use of prescription fish oil, Ezetimibe, and Bempedoic acid), provided there is sufficient number of subjects in the subgroup
- Type 2 diabetes (Yes, No)
- Age categories (21-<65,  $\geq 65$ ).

- Sex (male, female)
- Baseline weight <median and  $\geq$  median
- Region (US vs EU)
- TG responder at Week 8 (responder, non-responder)
- Use of background insulin medication (Yes/No) for insulin analysis only

Note, if the percentage of subjects within a certain subgroup is less than 33% (i.e., less than 6 of 18 subjects) of the overall cohort, only descriptive analysis will be performed.

More details of the analyses repeated in the above subgroups are described in [Section 7.5.1](#).

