## 7 STATISTICAL METHODS OF ANALYSES

### 7.1 GENERAL CONSIDERATIONS

The statistical analysis for this study will be performed by combining the main cohort and the fibrate extension cohort. A single database lock will be implemented.

All the tables and figures will be based on the pooled data from both cohorts, unless otherwise specified. One set of listings will be generated for the whole study.

In general, summaries and analyses will be presented by dose/treatment group. Descriptive statistics will be presented for demographics and baseline characteristics, safety endpoints, and PK and PD parameters. Continuous variables will be summarized by number of subjects and mean, SD/standard error, median, minimum, and maximum values. Minimum

---

and maximum will be presented to the same number of decimal places as reported/collected. One additional decimal place will be presented for mean and median. Two additional decimal places will be presented for SD up to a max of three decimal places.

Categorical variables will be summarized by number and percentage of subjects. Percentage will be presented to one decimal place. The number of missing values will be presented as a separate category with no percentage, but only if 1 or more subjects are missing data for the summary. Otherwise, all categories will be presented (even if no subjects are counted in the category). Counts of zero in any category will be presented without percentage.

All statistical tests will be 2-sided and tested at a statistically significant level of 0.05 without adjustment for multiplicity. Confidence intervals will be 2-sided 95%, unless stated otherwise. Two-sided p-values will be presented with four decimal places and values less than 0.0001 will be presented as <.0001.

Both reported units (CN) and SI units will be presented in listings.

Both CN and SI units will be used in lipid panel (TG and other lipids) tables and figures.

For the rest, only CN units will be used for tables and figures, unless otherwise specified. Insulin will be presented with conventional unit of  $\mu$ IU/mL;

The listings will only present non-imputed data.

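### The readable text of SAP 7.5.1 repeats the primary test within subgroup levels without comparing the effect between levels, so a single dose with a uniform effect will often look selective by chance

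*SAP*

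**What the plan says.** SAP 7.5.1 sets out the MMRM for percent change in TG at Week 8 and then says that "The primary efficacy analysis will be repeated in the subgroups", referring to SAP 4.7. SAP 7.5 defines the primary comparisons as all doses pooled v placebo and each dose v placebo. SAP 7.1 has every test two-sided and "tested at a statistically significant level of 0.05 without adjustment for multiplicity", with 95% confidence intervals.

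SAP 4.7 lists the TG stratum at 750 mg/dL, background lipid medication (yes/no, and by type), type 2 diabetes, age, sex, weight split at the median, region, and TG responder status at Week 8. Insulin use is listed for the insulin analysis only. Where a subgroup falls below 33%, which SAP 4.7 equates with fewer than 6 of 18 subjects, "only descriptive analysis will be performed". By implication, the larger subgroups receive the tested analysis.

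The only interaction in the readable model is visit by treatment. SAP 4.7 sends the reader to 7.5.1 for further detail on the subgroup analyses. There, the lines after the quoted sentence are blacked out, as is the sample code in Appendix 2. The table shells are a separate document.

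**The concern.** Testing each level of a factor separately gives two p-values, neither of which tests whether the effect differs between the levels. When each level has only moderate power, one p-value above 0.05 and one below it is a common result even if the true effect is identical. A reader of such a table may conclude that the drug works in one kind of patient and not in another.

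This matters because protocol 4.2 says the results are to inform dose selection for Phase 3, and because the analysis is repeated for single doses with about 18 subjects each. SAP 7.5 itself declines to stratify the single-dose comparisons because it expects them to be small. Splitting them into subgroup levels makes them smaller still.

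**Working it through.** **Inputs (SAP 3.5 and 7.1).** SD: "it is estimated that the SD of the percent change in TG at Week 8 is approximately 40" percentage points. Difference: 45 points, "assuming 50% reduction in BIO89-100 dose group and 5% in the placebo group". Group size: "With 18 subjects in the placebo group and each BIO89-100 active treatment group", with about 10% lost to follow-up. Two-sided 0.05, unadjusted.

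**Step 1: reproduce the plan's power.** The SAP says "there would be at least 86% power to detect a 45% difference in TG". For a two-sample t-test the noncentrality is 45 / (40 × √(1/n1 + 1/n2)) on n1 + n2 − 2 degrees of freedom. With 16 per group (18 less about 10%) it is 45 / 14.14 = 3.18 and power is 86.8%, which matches. With 18 per group and no loss, power is 90.6%.

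**Step 2: power within a level, one dose, 18 v 18, true difference 45 in both levels.**
- Even split, 9 v 9: 45 / 18.86 = 2.39, power 61.1%.
- Split at the 33% floor, 6 v 6: 45 / 23.09 = 1.95, power 42.1%.
- Its complement, 12 v 12: 45 / 16.33 = 2.76, power 75.0%.

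**Step 3: chance that exactly one of the two levels is significant**, p1(1 − p2) + p2(1 − p1).
- Even split: 2 × 0.611 × 0.389 = 0.475.
- 6/12 split: 0.421 × 0.250 + 0.750 × 0.579 = 0.54.

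With 16 evaluable per group the two figures are 49% and 55%.

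**Step 4: other comparisons, same method.** SAP 5.5 adds the fibrate-cohort placebo subjects to the placebo group and describes enrolment in that cohort as low. The placebo number therefore lies between 18 and the planned 36.

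| Drug v placebo | Power, even split | Exactly one, even split | Power, 33/67 split | Exactly one, 33/67 split |
|---|---|---|---|---|
| One dose, 18 v 18 | 61% | 47.5% | 42% and 75% | 54% |
| One dose, 18 v 36 | 75% | 37% | 56% and 87% | 45.5% |
| 27 mg pooled, 36 v 36 (as planned) | 91% | 17% | 75% and 97% | 27% |
| All doses, 72 v 18 | 84% | 27% | 66% and 93% | 36% |
| All doses, 90 v 36 (both cohorts full) | 98% | 4% | 89% and 99.6% | 11% |

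**Step 5: number of discordant factors, one dose, 18 v 18.** This was simulated with mutually independent two-level factors, split evenly or 33/67. The chance of two or more discordant factors is about 49% to 54% with three eligible factors, 55% to 66% with four and 70% to 78% with six. The documents do not say how many factors would be eligible or how they would split. Only weight is near even by construction.

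**Step 6: the between-level contrast.** For one dose at 18 v 18 with an even split, its standard error is 40 × √(4 × 1/9) = 26.7 points. Under a uniform effect, a test of this contrast is falsely significant for about 5% of factors, against the roughly 47.5% to 54% discordance above. Its power is low. If the 45-point effect were wholly absent in one level, 45 / 26.7 = 1.69, and power is about Φ(1.69 − 1.96) = 39%.

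**The case against.** **Redaction.** SAP 4.7 points to 7.5.1 for the subgroup details, and what follows the quoted sentence there is hidden. A reader might infer that the plan has no interaction test. The documents do not support that: it can be said only that none is readable. This objection stands, and it is why the sponsor's confirmation comes first.

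**The plan does not tell anyone to compare p-values.** Success is defined only on the pooled and single-dose comparisons, and SAP 7.1 provides for confidence intervals, so level-wise estimates may already be intended. This is fair. The plan does not prescribe the misreading. What remains is that the readable analysis supplies level-wise tests and no between-level estimate.

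**How far the figures reach.** A reader might infer that a uniform dose will usually look selective on several factors. That holds if about six or seven roughly even factors are eligible and placebo is near 18. With three factors, two or more discordant is about even odds. A reader might also multiply 7 factors × 2 levels × 5 comparisons = 70 tests and expect 70 × 0.05 = 3.5 false positives if no dose works. That count ignores the 33% rule and is an upper bound. For all doses pooled at full enrolment the problem is small.

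**An interaction test has its own faults.** It is imprecise here, and across six factors unadjusted interaction tests give a 25% to 28% chance of at least one false signal. Both points stand and shape the fix.

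**Conclusion.** The concern holds for the readable text, subject to what the redacted lines contain. For a single dose against about 18 placebo subjects, significance in one level only is close to a coin toss for each eligible factor (47.5% to 54%) when the true effect is uniform. It is about 37% to 45.5% with 36 placebo subjects, 27% to 36% for pooled drug at 72 v 18, and 4% to 11% at 90 v 36. The single-dose displays are therefore the main problem.

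The figures rest on a t-test in place of the MMRM, on levels balanced within each group, and on the plan's 45 points and SD 40. If covariate adjustment reduced the SD to 30, the single-dose range would be 26% to 37%, still well above the 5% of a direct between-level test. No firm statement can be made about the number of factors affected.

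**What to change.** 1. Ask the sponsor whether the redacted part of 7.5.1 already contains a between-level comparison. If it does, only the reporting points below remain.
2. For each baseline-defined factor with mutually exclusive levels, fit one MMRM on the whole Full Analysis Set with a treatment-by-subgroup-by-visit term and its lower-order terms. Report the Week 8 difference from placebo in each level with its 95% confidence interval, and the between-level difference with its 95% confidence interval. Label its p-value exploratory.
3. State that within-level p-values will not be used to claim or deny an effect in a subgroup.
4. Make pooled drug v placebo the main subgroup display. Give single doses as estimates with confidence intervals.
5. Treat each background medication type as its own yes/no factor, since the types can overlap.
6. Leave the Week 8 TG responder factor out of the treatment-effect subgroups. It is defined by the outcome, so a treatment interaction with it cannot be interpreted.

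The cost is SAP wording and table shells; no new data are needed. The drawback is imprecision: with a standard error of about 27 points for one dose at 18 v 18, the SAP should say that a non-significant interaction is not evidence of a consistent effect.
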